### **Vital signs**

All vital signs data will be listed by treatment group, On-treatment notable vital signs abnormalities will be summarized by treatment group.

### **12-lead ECG**

The notable ECG abnormalities will be summarized for following ECG variables,QT interval, RR interval, PR interval, QRS duration, heart rate, and Friedericia's QTc.

### **Clinical laboratory evaluations**

All laboratory data will be listed with abnormal values flagged.

All laboratory parameter values will be classified into one of the four mutually exclusive groups (low, normal, high, and low + high).

For selected laboratory parameters, the number and percentage of patients with newly occurring or worsening on-treatment laboratory abnormalities meeting the clinically notable will be summarized by laboratory parameter at any time-point over the treatment period, considering all post-baseline data from scheduled, unscheduled and premature discontinuation visits. Patients with any newly occurring or worsening on-treatment value meeting the clinically notable criteria will be counted under the applicable criteria.

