### **12.5.1 Safety Variables**

For all safety analyses, the safety set will be used. All listings and tables will be presented by treatment group. Safety summaries will be primarily based on on-treatment data with selected tables also presented for the all data after the first intake of study drug, while all databased safety data will be listed. The on-treatment period lasts from the date of first administration of study treatment to 30 days after the date of the last actual administration of any study treatment.

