The statistical analysis plan (SAP) describes all planned analyses for the Clinical Study Report (CSR) of study QAW039A2322, a phase IIIB, 16 week multicenter, randomized, double-blind, parallel-group, placebo-controlled study of fevipiprant once daily plus standard-of-care (SoC) for assessment of the efficacy in reduction of nasal polyp size in patients with nasal polyposis and concomitant asthma

The content of this SAP is based on the protocol of QAW039A2322 version v03.

The purpose of the statistical analysis plan is to describe the implementation of the statistical analysis planned in section 12 of the study protocol. Data will be analyzed by Novartis according to the data analysis section 12 of the protocol which is available in [Appendix 16.1.1 of the CSR](#). Important information is given in the following sections and the details will be provided, as applicable, in [Appendix 16.1.9 of the CSR](#).

[figure not shown]

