2.7.7 Laboratory data

Laboratory data consist of hematology and biochemistry measurements. Laboratory data measured after first intake of study drug and until the day after last intake of study drug are regarded as on-treatment data. Laboratory data measured more than 1 day after last intake of study drug are regarded as post-treatment data and will not be summarized. All data will be listed with abnormal values flagged.

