2.7.7.1 Summary of change from baseline

For continuous laboratory parameters, the on-treatment change from baseline to the worst post-baseline values (including values from post-baseline unscheduled and premature discontinuation visits) will be summarized by laboratory parameter and treatment group with standard descriptive statistics.

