2.14 Interim analysis

No interim analysis is planned.

3 Sample size calculation

Based on clinical judgement a mean reduction of 1.5 in polyp score (as measured by the NPS) can be expected with fevipiprant (450 mg and 150 mg) and SoC as compared to Placebo and SoC. Considering this factor, the sample size was calculated under an 80% power and 1.25% one sided alpha for comparison of each of the two dose levels of fevipiprant and SoC with placebo and SoC. A 10% dropout rate is considered as appropriate with reference to prior studies (omalizumab study by Gevaert et al 2013 and dupilumab study by Bachert et al 2016). From prior literature standard deviation of 1.8 is considered as appropriate for the change of score from baseline at 16 weeks in Nasal Polyp Score.

The sample size calculation was performed using the software PASS 2008 using inequality tests using difference of two independent means with equal variance.

The randomization will be performed in a 1:1:1 ratio for the two separate doses level of fevipiprant (450 mg and 150 mg) and the placebo arm. Under these assumptions (effect size = 1.5, equal SD = 1.8, power = 80% for each arm individually, one-sided alpha = 0.0125 and dropout = 10%), the total sample size yielded was 93 with 31 patients in each arm. The sample size provides a power of 80% for each comparison but since we will be testing correlated hypothesis using a Dunnett's test, this is a lower bound on the power. The real power is expected to be higher if in at least one of the 2 dosages i.e. fevipiprant 150 mg or fevipiprant 450 mg, the standardized effect size (in other words, keeping the assumption of an SD of 1.8 in each group) is equal to the clinically significant value of 1.5 and there is some treatment benefit in the other groups as well. However, if the effect size is equal to 1.5 in both of the groups, the power will be substantially higher i.e. around 93%.

4 Change to protocol specified analyses

Not Applicable

5 Appendix

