5.3 Laboratory parameters derivations

The following table shows the criteria for clinically notable laboratory values. Not all parameters have notable criteria defined.

Table 5.3.1 Direction of interest for worst case value for laboratory parameters

Laboratory Parameter	Direction of interest for worst case value
A. Hematology	
Basophils	High
Eosinophils	High
Hematocrit	Low
Hemoglobin	Low
Lymphocytes	Low and high
Monocytes	High
Neutrophils	Low and high
Platelets	Low and high
RBC	Low
WBC total	Low and high
B. Chemistry	
Albumin	Low
Sodium	Low and High
Alkaline Phosphatase	High
ALT/SGPT	High
AST/SGOT	High
Bilirubin Total	High
Blood Urea Nitrogen (BUN)	High
CPK	High
Creatinine	High
Gamma GT	High
Glucose	Low and high
Potassium	Low and high
Uric acid	High

Table 5.3.2 Clinical notable criteria for selected laboratory tests

Laboratory parameter (unit)	Bound for notably low values	Bound for notably high values
Hematology		
Hematocrit (v/v)		
Male 12-17	0.34	
Male 18-65	0.37	
Male >=66	0.34	
Female 12-65	0.32	
Female >=66	0.31	

Laboratory parameter (unit)	Bound for notably low values	Bound for notably high values
Hemoglobin (g/L)		
Male 12-17	100	
Male >=18	110	
Female	95	
Thrombocytes (x10E ⁹ /L)	75	700
WBC's (x10 ⁹ /L)	2.8	16.0
Chemistry		
Alkaline Phosphatase (IU/L)	-	3xULN
Total Bilirubin (µmol/L)	-	34.2
Creatinine (µmol/L)		176.8
Potassium (mmol/L)	3	6
Glucose (mmol/L)	2.78	9.99
ALT/SGPT (U/L)	-	3 x ULN
AST/SGOT (U/L)	-	3 x ULN
BUN/ Urea (mmol/L)		9.99
Sodium (mmol/L)	125	160
Gamma GT (U/L)		3 x ULN
CPK (IU/L)		4 x ULN

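### The SAP omits the protocol's low / normal / high / low + high laboratory classification and declares no change, so 22 of 37 routine blood parameters have no by-arm laboratory count of abnormal patients

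*Protocol*

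**What the plan says.** The protocol's paragraph on clinical laboratory evaluations (section 12.5.1) plans three things:

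1. A listing of all laboratory data with abnormal values flagged.
2. A classification: "All laboratory parameter values will be classified into one of the four mutually exclusive groups (low, normal, high, and low + high").
3. For selected parameters, the number and percentage of patients with newly occurring or worsening clinically notable values.

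The opening of the same section adds: "All listings and tables will be presented by treatment group".

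SAP section 2.7.7 plans the following for laboratory data:

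- Listing: "All data will be listed with abnormal values flagged".
- Summary: "For continuous laboratory parameters, the on-treatment change from baseline to the worst post-baseline values", with standard descriptive statistics by treatment group.
- Counts of patients meeting the notable criteria in Table 5.3.2. The SAP says of these criteria: "Not all parameters have notable criteria defined".
- Box plots over time of change from baseline for ALT, AST, their ratio, total bilirubin, creatinine and albumin.

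The SAP introduction gives the document's purpose as "to describe the implementation of the statistical analysis planned in section 12 of the study protocol". SAP section 4, headed "Change to protocol specified analyses", is marked as not applicable.

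**The concern.** Item 2 of the protocol's list has no counterpart in the SAP. It is the only planned laboratory output that covers every parameter and sorts results against the normal range. Without it, the only laboratory count of patients by arm is the notable-value count, which covers fewer than half of the routine parameters and, where a bound is a multiple of ULN, starts well above the normal limit.

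The stake is safety reporting in a small trial of about 31 patients per arm. If a few more patients on one arm have neutrophils, albumin, calcium or lipase out of range, no planned laboratory table counts them. A reader would have to build the comparison from listings. Because SAP section 4 declares no change, nothing tells that reader that a protocol-specified analysis was not done.

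**Working it through.** The plan gives no figure to reproduce here, so the check is a comparison of texts and a count of parameters.

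**Step 1. Match outputs.**

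| Protocol 12.5.1 | SAP 2.7.7 and 5.3 |
|---|---|
| Flagged listing | Present (2.7.7) |
| Low / normal / high / low + high for all parameters | Absent |
| Notable-value counts, selected parameters | Present (2.7.7.2, Table 5.3.2) |
| Not planned | Added: change to worst value (2.7.7.1), box plots (2.7.7.2) |

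The nearest trace is SAP Table 5.3.1, where some entries read low and high. That table says which extreme is the worst value; it does not classify patients or values.

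**Step 2. Is item 2 more than a listing flag?** Flagging is a separate sentence in the protocol. A single value cannot be both low and high, so the fourth group makes sense only for a patient with several values. Table 8-1 schedules on-treatment haematology and chemistry at Weeks 8 and 16, so a patient could fall into it. The natural reading is a per-patient table.

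**Step 3. Count the parameters.**

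- Protocol Table 8-4, haematology: 8 indices + 5 differential counts = 13.
- Protocol Table 8-4, chemistry: 24, leaving out HbA1c (screening and end of treatment only) and the reflex tests CK-MB and troponin I.
- Total: 13 + 24 = 37, or 38 with HbA1c. Urinalysis and coagulation are not in this count.
- SAP Table 5.3.2, notable bounds: 4 haematology + 11 chemistry = 15, all among the 37.
- No notable bound: 37 − 15 = 22, or 38 − 15 = 23 with HbA1c.

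The 22 are MCH, MCHC, MCV, red cells and the five differential counts (9), plus albumin, LDH, calcium, magnesium, phosphorus, chloride, direct bilirubin, cholesterol, total protein, triglycerides, uric acid, amylase and lipase (13). 9 + 13 = 22.

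**Step 4. The 15 with bounds.** Five bounds are multiples of ULN: ALP, ALT, AST and GGT at 3 x ULN, and CPK at 4 x ULN. Values above ULN but short of those multiples enter no laboratory count. The other ten bounds are absolute figures. The documents give no normal ranges, so the width of the gap cannot be stated for those ten.

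**Step 5. What still shows such values.** SAP 2.1.2 defines descriptive statistics to include minimum and maximum, so the worst-change summary shows the extreme changes in each arm. One limit applies: Table 5.3.1 gives a worst direction for 23 parameters, which are the 15 with bounds plus 8 of the 22. For the remaining 22 − 8 = 14 the SAP does not say which extreme is the worst. Under protocol section 10.1.1, abnormal values that cause symptoms, need therapy or are clinically significant are adverse events. If they start on treatment, they enter the by-arm tables of SAP 2.7.5.

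**The case against.** The best defence is that the protocol promises little and the SAP covers most of it. The sentence says only that values will be classified. It names no shift table and no baseline cross-tabulation, and the phrase about number and percentage of patients appears only for notable values. The SAP also says that analysis follows protocol section 12, which could be read as carrying the classification in by reference. Abnormal values remain listed and flagged, the extremes are shown by arm, and clinically significant ones reach the adverse event tables.

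Much of this stands, and it rules out several stronger readings that a reader might infer:

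- **That the protocol promised a shift table.** It did not. A baseline-by-worst table is one sensible way to carry out the commitment.
- **That mild abnormalities would be invisible, or in no count at all.** They are listed and flagged, and those that qualify as adverse events are counted there. What is missing is a laboratory count.
- **That all 15 notable bounds lie far outside normal.** The documents show this only for the five stated as multiples of ULN.
- **That the missing table would count rises above 2 x ULN**, the level used in the screening exclusions for ALT or AST and for CK in statin users. It would not, because 1.1 x ULN and 2.9 x ULN both fall under high.

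The general reference to section 12 does not cure the omission. It specifies no table, and the SAP presents itself as describing all planned analyses for the study report.

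**Conclusion.** The point holds as a gap between protocol and SAP in safety reporting. A protocol-specified classification of all laboratory parameters has no implementation in the SAP, and SAP section 4 records no change. As planned, 22 of 37 routine blood parameters (23 of 38 with HbA1c) have no laboratory count of abnormal patients by arm. For the other 15, results between the normal limit and the notable bound are not tabulated against the normal range.

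This rests on reading the protocol sentence as a per-patient table by treatment group. The low + high group and the by-group statement in section 12.5.1 both support that reading. The count depends on the stated exclusions (reflex tests, urinalysis, coagulation). The primary analysis is untouched and no data are lost. It should be corrected before database lock but does not threaten the trial's main conclusion.

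**What to change.** In SAP section 2.7.7, add a table by treatment group on the Safety Set for every parameter with a normal range. It should count patients by on-treatment category (normal, low only, high only, low + high), use scheduled, unscheduled and premature-discontinuation visits, and apply the same on-treatment window as the notable-value count. Showing these categories against the baseline category, with a group for missing baseline, is preferable but goes beyond what the protocol requires.

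In protocol section 12.5.1, reword the sentence so that patients, not values, are classified.

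If the classification was dropped on purpose, record the removal and the reason in SAP section 4 instead.

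The cost is one standard table and a longer safety output. No new data are needed, because protocol Appendix 1 (section 16.1) already has the central laboratory flag values outside the normal range.

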## **12.7 Interim analyses**

No formal interim analysis will be performed in this trial.

## **12.8 Sample size calculation**

### **12.8.1 Primary endpoint(s)**

Based on clinical judgement a mean reduction of 1.5 in polyp score (as measured by the NPS) can be expected with fevipiprant (450 mg and 150 mg) and SoC as compared to Placebo and SoC. Considering this factor, the sample size was calculated under an 80% power and 1.25% one sided alpha for comparison of each of the two dose levels of fevipiprant and SoC with placebo and SoC. A 10% dropout rate is considered as appropriate with reference to prior studies (omalizumab study by [Gevaert et al 2013](#) and dupilumab study by [Bachert et al 2016](#)). From prior literature standard deviation of 1.8 is considered as appropriate for the change of score from baseline at 16 weeks in Nasal Polyp Score.

The sample size calculation was performed using the software PASS 2008 using inequality tests using difference of two independent means with equal variance.

The randomization will be performed in a 1:1:1 ratio for the two separate doses level of fevipiprant (450 mg and 150 mg) and the placebo arm. Under these assumptions (effect size = 1.5, equal SD = 1.8, power = 80% for each arm individually, one-sided alpha = 0.0125 and dropout = 10%), the total sample size yielded was 93 with 31 patients in each arm.

The sample size provides a power of 80% for each comparison but since we will be testing correlated hypothesis using a Dunnett's test, this is a lower bound on the power. The real power is expected to be higher if in at least one of the 2 dosages i.e. fevipiprant 150 mg or fevipiprant 450 mg, the standardized effect size (in other words, keeping the assumption of an SD of 1.8 in each group) is equal to the clinically significant value of 1.5 and there is some treatment benefit in the other groups as well. However, if the effect size is equal to 1.5 in both of the groups, the power will be substantially higher i.e. around 93%

## **13 Ethical considerations and administrative procedures**

### **13.1 Regulatory and ethical compliance**

This clinical study was designed and shall be implemented, executed and reported in accordance with the ICH Harmonized Tripartite Guidelines for Good Clinical Practice, with applicable local regulations (including European Directive 2001/20/EC, US CFR 21), and with the ethical principles laid down in the Declaration of Helsinki.

### **13.2 Responsibilities of the investigator and IRB/IEC**

Before initiating a trial, the Investigator/institution must obtain approval/favorable opinion from the Institutional Review Board/Independent Ethics Committee (IRB/IEC) for the trial protocol, written informed consent form, consent form updates, subject recruitment procedures (e.g., advertisements) and any other written information to be provided to subjects. Prior to study start, the Investigator is required to sign a protocol signature page confirming his/her agreement to conduct the study in accordance with these documents and all of the instructions and procedures found in this protocol and to give access to all relevant data and records to Novartis monitors, auditors, Novartis Quality Assurance representatives, designated agents of Novartis, IRBs/IECs, and regulatory authorities as required. If an inspection of the clinical site

is requested by a regulatory authority, the Investigator must inform Novartis immediately that this request has been made.

### **13.3 Publication of study protocol and results**

The protocol will be registered in a publicly accessible database such as clinicaltrials.gov and as required in EudraCT. In addition, after study completion (**defines as last patient last visit**) and finalization of the study report the results of this trial will be submitted for publication and posted in a publicly accessible database of clinical trial results, such as the Novartis clinical trial results website and all required Health Authority websites (e.g. Clinicaltrials.gov, EudraCT etc.) .

For details on the Novartis publication policy including authorship criteria, please refer to the Novartis publication policy training materials that were provided to you at the trial Investigator meetings

### **13.4 Quality Control and Quality Assurance**

Novartis maintains a robust Quality Management System (QMS) that includes all activities involved in quality assurance and quality control, to ensure compliance with written Standard Operating Procedures (SOPs) as well as applicable global/local GCP regulations and ICH Guidelines.

[figure not shown]
Audits of Investigator sites, vendors, and Novartis systems are performed by auditors, independent from those involved in conducting, monitoring or performing quality control of the clinical trial. The clinical audit process uses a knowledge/risk based approach.

Audits are conducted to assess GCP compliance with global and local regulatory requirements, protocols and internal SOPs, and are performed according to written Novartis processes

## **14 Protocol adherence**

This protocol defines the study objectives, the study procedures and the data to be collected on study participants. Additional assessments required to ensure safety of subjects should be administered as deemed necessary on a case by case basis. Under no circumstances including incidental collection is an Investigator allowed to collect additional data or conduct any additional procedures for any purpose involving any investigational drugs under the protocol, other than the purpose of the study. If despite this interdiction prohibition, data, information, observation would be incidentally collected, the Investigator shall immediately disclose it to Novartis and not use it for any purpose other than the study, except for the appropriate monitoring on study participants.

Investigators ascertain they will apply due diligence to avoid protocol deviations. If an Investigator feels a protocol deviation would improve the conduct of the study this must be considered a protocol amendment, and unless such an amendment is agreed upon by Novartis and approved by the IRB/IEC and health authorities, where required, it cannot be implemented.

## **14.1 Protocol Amendments**

Any change or addition to the protocol can only be made in a written protocol amendment that must be approved by Novartis health authorities where required, and the IRB/IEC prior to implementation.

Only amendments that are required for subject safety may be implemented immediately provided the health authorities are subsequently notified by protocol amendment and the reviewing IRB/IEC is notified.

Notwithstanding the need for approval of formal protocol amendments, the Investigator is expected to take any immediate action required for the safety of any subject included in this study, even if this action represents a deviation from the protocol. In such cases, Novartis should be notified of this action and the IRB/IEC at the study site should be informed according to local regulations.

## 16 Appendices

[figure not shown]
### 16.1 Appendix 1: Clinically notable laboratory values and vital signs

The central laboratory will flag laboratory values falling outside of the normal ranges on the central laboratory reports. Investigators are responsible for reviewing these abnormal values for clinical significance, signing the laboratory reports to indicate their review, and reporting values considered clinically significant in the appropriate electronic case report form (eCRF).

Any clinically significant abnormal laboratory value should be evaluated and followed-up by the Investigator until normal or a cause for the abnormality is determined.

See [Section 16.2](#) for specific liver event and laboratory test trigger definitions and follow-up requirements. See [Section 16.3](#) for specific renal alert criteria and actions.

For electrocardiograms (ECGs), a notable QTc value is defined as a QTcF (Fridericia) interval of  $\geq 450$  msec for males or  $\geq 460$  msec for females. All ECGs will be assessed locally at site and with assessment of clinical relevance and continuance of the patient being confirmed by the Investigator.

## 16.2 Appendix 2: Liver event and Laboratory trigger Definitions and Follow-up Requirements

[figure not shown]
**Table 16-1 Liver Event and Laboratory Trigger Definitions**

	Definition/ threshold
LIVER LABORATORY TRIGGERS	
 
3 x ULN < ALT / AST ≤ 5 x ULN
 
1.5 x ULN < TBL ≤ 2 x ULN
 

LIVER EVENTS	
 
ALT or AST > 5 × ULN
 
ALP > 2 × ULN (in the absence of known bone pathology)
 
TBL > 2 × ULN (in the absence of known Gilbert syndrome)
 
ALT or AST > 3 × ULN and INR > 1.5
 
Potential Hy's Law cases (defined as ALT or AST > 3 × ULN and TBL > 2 × ULN [mainly conjugated fraction] without notable increase in ALP to > 2 × ULN)
 
Any clinical event of jaundice (or equivalent term)
 
ALT or AST > 3 × ULN accompanied by (general) malaise, fatigue, abdominal pain, nausea, or vomiting, or rash with eosinophilia
 
Any adverse event potentially indicative of a liver toxicity*
 

* These events cover the following: hepatic failure, fibrosis and cirrhosis, and other liver damage-related conditions; the non-infectious hepatitis; the benign, malignant and unspecified liver neoplasms TBL=total bilirubin; ULN=upper limit of normal
	

